**Table 1. Study Timeline**

Study Year	Year 1				Year 2				Year 3				Year 4				Year 5							
Year	2017				2018				2019				2020				2021				2022			
Quarter	1	2	3	4	1	2	3	4	1	2	3	4	1	2	3	4	1	2	3	4	1	2	3	4
IRB/IND/startup																								
Recruitment & Enrollment																								
Final Study Visits																								
Metabolomics analysis																								
DSMB Meetings																								
Data analysis																								
R03 (metabolomics); R01																								
Manuscripts																								

**D. Description, Risks and Justification of Procedures and Data Collection Tools:**

1. **BODY COMPOSITION ASSESSMENT: The PeaPod** provides a reliable, non-invasive, quantitative assessment of fat mass and non-fat mass utilizing air-displacement plethysmograph technology in infants weighing less than 10 kilograms. This instrument has been validated with other methods of body composition assessment, such as deuterium dilution and dual-energy X-ray absorptiometry, and normative values for healthy, term, average-gestational age males are published from birth through 6 months. The PeaPod is safe and comfortable for infants and takes less than 10 minutes to perform, with the actual test less than 2 minutes. The chamber is heated and has white noise that distracts most infants. The infant can move, cry, and urinate during the assessment, therefore it is very “baby friendly”. However, the PeaPod may cause temporary distress to the infant as they are unclothed and not swaddled. A blinded study investigator will perform this assessment at all study visits. Age-specific Z-scores for %BF will be calculated from published data.

*Likelihood of experiencing any risk: low*

*Likelihood of experiencing serious risk: very low*

*Alternatives:* Body composition can be measured by dual-energy x-ray absorptiometry (DXA), however DXA does involve low amounts of radiation exposure in addition to laying on a flat surface similar to the PeaPod. DXA also is best when the subjects lie still, which is challenging for young infants. Body fat can also be estimated with skin fold calipers, however this is generally not as accurate as the PeaPod and does have the risk of temporary discomfort as well. Therefore, we have determined the PeaPod has the least risk to obtain our outcome of interest.

*Protections against risk:* When possible, we will perform the PeaPod assessment when the infant is awake and content having recently eaten. We will encourage the parents to bring a familiar toy that may distract the infant if he becomes distressed. We would encourage comforting/consoling after the procedure if temporary distress was experienced. Parents will be present during the PeaPod.

2. **NEURODEVELOPMENTAL ASSESSMENT:** The Alberta Infant Motor Scale (AIMS), Peabody Developmental Motor Scales -2 (PDMS-2), and the Bayley Scales of Infant Development – 3rd edition will be performed by a psychometrist trained to administer these standardized neurodevelopmental assessments. The **AIMS** is a performance-based and norm-referenced measure of infant gross motor maturation from birth to 18 months. It is intended to evaluate gross motor development over repeated assessments and has good reliability and predictive validity for later gross motor development. In a systematic review of neurodevelopmental tests, the AIMS had the best psychometric properties and clinical utility. The **PDMS-2** is a standardized assessment for infant development and includes six subtests to assess gross and fine motor scales from birth to 5 years. It is one

of the most common tools for discriminating normal from abnormal infant motor development. This instrument was chosen as a broad assessment of motor development with normative reference data, and strongly correlates with other motor assessments. The **Bayley 3** is a comprehensive standardized assessment for infant development containing three domains: Cognitive, Language, and Motor. The Bayley-3 is widely used to diagnosis developmental delays up to 3.5 years of age. Finally, a parent will complete the Adaptive Behavior Assessment System, 3rd edition (**ABAS 3**), a validated measure of adaptive skills across the lifespan, including infancy. The ABAS incorporates early developmental skills in areas such as feeding, sleep, play, self-regulation, and social development. The primary risk of the developmental evaluation is identification of developmental delays that may warrant further evaluation and/or intervention. This may cause psychological distress to the parent.

*Likelihood of experiencing any risk: low*

*Likelihood of experiencing serious risk: very low*

*Alternatives: None identified.*

*Protections against risk:* Parents will be made aware of the high prevalence of at least mild developmental delays in XXY. Parents will be present during the evaluation. If delays are identified, the study team will disclose this to the parent(s) in a private area with specific recommendations for next-steps, potentially including referrals and/or resources.

**3. VENIPUNCTURE.** Venous blood samples will be drawn in the morning a minimum of 180 minutes after eating (fasting for an infant.) The collection of blood samples may result in temporary discomfort, bruising, bleeding, and on rare occasions, infection. Standard hospital precautions for venipuncture will be followed. Anemia is also a risk; the routine guidelines in our Pediatric CTSC are 2.5 ml/kg per blood draw. We will draw 8 ml of blood per visit. If the subject is <3.2kg on the first visit we will reduce the amount of blood to be drawn.

*Likelihood of experiencing any risk: moderate (temporary discomfort).*

*Likelihood of experiencing serious risk: very low*

**Hormones.** Serum will be processed and stored at -80 degrees until batch analysis for quantification of LH, FSH, total and free T by liquid chromatography tandem mass spectroscopy (LC/MS), AMH, INHB, estradiol and leptin. Serum testosterone, inhibin B, AMH, estradiol and gonadotropins at baseline will allow us to assess endogenous testicular function. Hormone concentrations after testosterone exposure will serve as a short-term safety measure of testicular function. Exploratory aims may include looking at whether baseline serum testosterone predicts change in our outcomes after testosterone exposure. Leptin is biomarker of adiposity and will be used as a secondary measure to support our Peapod findings. Our previous work has shown that leptin concentrations are higher in boys with Klinefelter syndrome and this study will be the first to assess this in infants and explore how testosterone supplementation alters leptin in this population. Finally, we will measure serum lipids (triglycerides and HDL) and insulin as markers of insulin resistance using Trig/HDL ratio and 1/insulin as estimates. There are very limited validated assessments of cardiometabolic health in infants, therefore these data will largely be exploratory. If blood volume is limited, the order of priority for serum measurements will be as follows: Testosterone > inhibin B > leptin > gonadotropins > AMH > lipids > insulin > estradiol. Additional serum may be saved for future analyses.

**Metabolomics.** Plasma will be processed and stored until batch analysis using electrospray tandem mass spectroscopy per standard protocols in the [name] Lab. Concentrations of each metabolite of interest will be quantified: acylcarnitines (short, medium, and long-chain) and BCAA (leucine/isoleucine and valine). Non-targeted measurements of metabolites using liquid chromatography/mass spectroscopy will be analyzed using a well-established platform for comprehensive unbiased metabolomics resulting in the relative quantification of over 4,000 metabolites, including amino and organic acids, glycerolipids, sphingolipids, and sterols. Compound identification will be done through an in-house database. Principal components analysis will be used to consolidate the raw metabolite variables into clusters. We will use these data to determine pathways that are up or down regulated with exogenous testosterone. Additional plasma may be saved for future analyses.

**DNA and RNA storage.** Samples will be collected, processed, and stored at -80 degrees for future analyses.

4. **URINE AND STOOL COLLECTION.** Urine will be collected by placing cotton balls in the diaper immediately after arriving at the study visits. Cotton balls become saturated when the infant urinates, and the urine will be squeezed out into a cryovial for storage to later measure hormones and metabolites. If the infant stools during the study visit, a stool sample will be collected from the diaper and stored for future microbiome analysis. Both urine and stool samples will be stored as part of this protocol, with future plans to use these stored specimens to measure hormones and metabolomics (urine) and assess the microbiome (stool) both to look for differences unique to XXY infants and to assess acute changes with testosterone exposure on these measures. No invasive methods for obtaining urine or stool will be used in this protocol, therefore no risk to the participant is identified.

*Likelihood of experiencing any risk:* very low

*Likelihood of experiencing serious risk:* very low

*Alternatives:* There are no less-invasive alternatives to assess the microbiome or metabolites.

5. **HISTORY AND PHYSICAL EXAM.** A medical history for the participant including intrauterine history, birth history, medical and developmental history, and feeding history will be obtained from the parent at the first study visit by a member of the study team. Subsequent study visits will collect interim/updates to these histories as well as any potential study adverse events. A physical exam will be completed by the PI (in her absence, one of the other physicians on the protocol). Weight will be recorded to the nearest 0.01 kg. Length measurements will be recorded to the nearest 0.1 cm. Testicular volume to the nearest mL will be assessed using a Prader orchimeter. If testes are significantly less than 1mL, an estimate of 0.5mL will be used.

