### Specific Aim 1: To quantify the short-term effect of T in infants with XXY on cardiometabolic outcomes.

**Hypothesis:** Percent body fat (%BF) will follow a normal trajectory in treated infants, while infants not receiving T will have greater %BF. **Approach:** In the TESTO: Testosterone Effects on Short-Term Outcomes trial, infants with XXY (n=75) age 4-12 weeks will be randomized 1:1 to receive 25mg intramuscular T injections every 4 weeks for 3 doses or placebo. %BF will be assessed by air displacement plethysmography at baseline, 12 weeks, and 24 weeks. The primary outcome is change in %BF z-scores at 12 weeks between groups (powered to detect a difference of 0.5SD). Infants initially receiving placebo will get T in the second half of the study (12-24 weeks). Secondary outcomes include change %BF z-scores from 12-24 weeks, growth parameters, and serum leptin.

**Specific Aim 2: To quantify the short-term effects of T in infants with XXY on neurodevelopment, gonadal function and safety outcomes.**

**Hypothesis:** (1): XXY infants receiving T will have greater gains in standard scores on early motor skills, emerging language, and adaptive functioning. (2): T treatment will not impair gonadal function, as measured by gonadotropins and biomarkers of Sertoli cell function. (3): There will be no serious adverse outcomes associated with T treatment in infants with XXY. **Approach:** Infants from Aim 1 will be given standardized neurodevelopment assessments at baseline, 12 and 24 weeks. Serum hormone biomarkers of gonadal function will also be obtained at these times. Adverse events will be monitored throughout the study.

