## IV. Research Methods

### A. Outcome Measure(s):

#### Primary for Specific Aim 1

Change in %BF z-scores from baseline to 12 weeks (per PeaPod)

#### Primary for Specific Aim 2

Change in motor composite percentile on the AIMS assessment from baseline to 12 weeks

#### Primary for Specific Aim 3

Change in C14:1 long chain acylcarnitine (LCAC) from baseline

**Secondary outcomes:** Change in %BF z-scores from 12 to 24 weeks; change in anthropometric measurements from baseline to 12 and 24 weeks; change in gross and fine motor scaled scores from the PDMS; cognitive and language scores on the Bayley; adaptive functioning from the ABAS; serum hormones, lipids, BCAA, LCAC, and pathway analysis of untargeted metabolomics; urine metabolites; and number and type of adverse events.

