### B. Description of Population to be Enrolled:

A total of 75 infants with XXY will be enrolled. We will include all races, ethnicities, and languages.

*Inclusion criteria:* Male infants with 47,XXY karyotype identified prenatally who are 4-12 weeks old (31 to 90 days of age). 47,XXY must be from a diagnostic test such as CVS, amniocentesis, or post-natal blood/tissue. Non-invasive prenatal screening results alone will not be accepted.

*Exclusion criteria:*

- 1) >20% mosaicism for a normal cell line
- 2) Gestational age at birth <36 weeks
- 3) Birth weight <2.5thile or >97.5thile for age (small or large for gestational age)
- 4) History of thrombosis in self or a first degree relative
- 5) Exposure to androgen therapy outside the study protocol
- 6) Use of medications known to affect body composition, such as growth hormone or insulin
- 7) Known allergy to the testosterone cypionate solution components including benyl benzoate, benzyl alcohol, or cottonseed oil

Involving children is imperative as boys <18 years of age with XXY are much a different population than adult men with XXY. Men with XXY have been shown to have a high prevalence of type 2 diabetes, metabolic syndrome, fatty liver disease, and psychosocial difficulties. Clearly these processes begin in childhood. The potential to intervene in a preventative fashion, prior to the onset of disease, is more promising and productive than trying to treat pre-existing disease. Infant boys are exposed to endogenous testosterone in the first few months of life known as the “mini-puberty period of infancy.” Animal and human studies suggest this is a critical period for biologic programming, and therefore cannot be replicated at any other point in life. Including children in this study design allows us to investigate testosterone as a targeted intervention at this critical time point with evaluation of early markers of disease and disability. The ultimate goal is to improve the lives of children and adults with this condition.

The age of the infants at enrollment was chosen 1) to allow assessment of testicular function during the expected mini-puberty period of infancy, 2) to assure visits 2 and 3 will be completed before the infant is 10kg, as this is the upper weight limit for the PeaPod (our body composition assessment tool), and 3) feedback from parents.

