**Study Procedures.**

1. **Study Visits.** There will be a total of three in-person study visits:

- Visit 1, week 0 (4-12 weeks of age)
- Visit 2, week 12 ± 10 days (~5 months of age)
- Visit 3, week 24 ± 10 days (~8 months of age)

Procedures during the study visits will take a total of approximately 3 hours and will usually be completed on the same day. If all procedures cannot be scheduled for the same day they will be scheduled for two days in a row. The study visits will include all of the following:

- Infant and maternal history collection including medications, therapies, infant feeding method, and adverse reactions (~30 minutes)
- Physical examination including length, weight, head circumference, arm span, waist circumference, stretched penile length, Tanner staging, and testicular size by Prader orchidometer (~30 minutes)
- Quantified body composition assessment by the PeaPod (~30 minutes)
- Standardized neurodevelopmental assessment (~30 minutes)
- Morning venous blood draw following a minimum of 180 minutes fasting (~30 minutes)
- Non-invasive urine and stool sample collection (~10 minutes)
- Visit 1 only: intramuscular injection and teach

	Visit 1: Week 0		Visit 2: Week 12		Visit 3: Week 24
Group A n=30		T T T		P P P	
Group B n=30		P P P		T T T	
Study Activity					
Medical History	X		X		X
Physical Exam	X		X		X
PeaPod	X		X		X
Developmental Eval	X		X		X
Blood draw	X		X		X
Urine/stool collect.	X		X		X
Safety Assessment	X	X X	X	X X	X

**Figure 6.** Overall study design, timeline and assessments. T=testosterone, P=placebo

2. **Injections/Intervention.** Participants in this study will receive a total of 6 injections. 25 mg testosterone cypionate (200 mg/mL) or placebo (saline) will be given via intramuscular injection every 4 weeks (study weeks 0, 4, 8, 12, 16, and 20). The total volume of each injection will be 0.125 mL. The first shot for all participants will be administered at CHCO before the end of study visit #1 and the infant will be observed for 15 minutes. Parents will elect to either have the 5 subsequent injections given by a nurse at CHCO or to give them at home themselves. If they elect to give them at home, a nurse in the Pediatric CTRC or in Endocrinology will teach the parents how to administer the shots. Parents will receive an automated email reminder 24 hours before the next injection is due. Parents will keep an administration log to document the injection was given.

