**F. Data Analysis Plan:**

The primary outcome for **specific aim 1** is the change in %BF z-scores between baseline and 12 weeks between treatment groups. Z-scores will be calculated using published norms for age, and the difference between groups will be assessed with a two-sided t-test using an alpha of 0.05. Allowing for a 10% drop-out rate, a sample size of 27 in each group gives us 80% power to detect a difference down to 0.5 z-score change between groups, and >99% power to detect the change score we observed in our pilot study (1.0 z-score change) assuming a variance of 0.65 per our pilot data. We will next use regression models with treatment group, baseline %BF, age of enrollment and feeding method as explanatory variables to assess absolute %BF at 12 weeks. Secondary analyses will include change in %BF z-scores from 12 to 24 weeks 1) in the group receiving T first (are the effects of T maintained or lost?) and 2) in the group receiving T second (does later T have the same effect?). We will analyze anthropometric measurements and serum biomarkers similarly.

For **specific aim 2**, the change in standard scores on developmental assessments will be analyzed in a similar fashion as in specific aim 1. Based on our pilot data, our sample size will yield 80% power to detect a difference between groups of 23 percentile points on the AIMS composite. Secondary analysis will include the changes in scaled scores for the individual Peabody domains and AIMS subtests, the Bayley composite scores, and the ABAS composite at 12 and 24 weeks. Gonadal function and safety outcomes will be compared between subjects on T and placebo using descriptive statistics.

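### The week-24 body-fat z-score has no usable reference: the named norms stop at 6 months, and Visit 3 falls at 6.2 to 8.8 months of age

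*Combined protocol and SAP*

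**What the plan says.** Section IV.D, item 1 (body composition assessment), describes the PeaPod and cites reference 67 for its norms: "normative values for healthy, term, average-gestational age males are published from birth through 6 months". The same item adds that "Age-specific Z-scores for %BF will be calculated from published data", citing the same reference. The Data Analysis Plan (IV.F) repeats this single source: "Z-scores will be calculated using published norms for age".

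Infants enter at "4-12 weeks old (31 to 90 days of age" (IV.B). The visit schedule in IV.C reads "Visit 3, week 24 ± 10 days (~8 months of age".

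A week-24 z-score is needed in four places. Specific Aim 1 states "Secondary outcomes include change %BF z-scores from 12-24 weeks". The outcome list in IV.A has "Change in %BF z-scores from 12 to 24 weeks". The Data Analysis Plan examines that change separately in each randomised group. Table 2 lists a week-24 %BF z-score outcome as well, but as change from baseline.

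IV.B justifies the entry age partly by the PeaPod weight limit, "to assure visits 2 and 3 will be completed before the infant is 10kg". It does not mention the age limit of the norms.

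**The concern.** The protocol places the last body-composition visit at about 8 months and scores it against norms that, by its own account, end at 6 months. It does not say how a z-score is to be obtained beyond that age.

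The Data Analysis Plan uses the change from week 12 to week 24 for two questions: whether the effect persists after testosterone stops in the early-treatment group, and whether testosterone given later works as well in the other group. Visit 2 lies inside the norms and Visit 3 outside. Any error in the extrapolated reference mean at Visit 3 therefore passes in full into each group's mean change, where it could look like loss, persistence or a new effect. It also passes in full into a comparison of the late group's 12-24 week change with the early group's 0-12 week change. It would largely cancel in a comparison of the two groups at the same visit.

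A reference chosen after unblinding could also be influenced by the results.

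**Working it through.** **Inputs**

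- Upper age of the norms: 6 months (IV.D, item 1). With 30.4375 days per month, 6 months = 182.6 days and 7 months = 213.06 days.
- Entry age: 31 to 90 days (IV.B). The same sentence also says 4-12 weeks, which is 28 to 84 days.
- Visit 2: day 84 ± 10. Visit 3: day 168 ± 10 (IV.C).

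**Formula.** Age at visit = entry age + visit day ± 10.

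**The plan's own ages.** The midpoint of entry is (31 + 90)/2 = 60.5 days.

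- Visit 2: 60.5 + 84 = 144.5 days = 4.75 months. The protocol says about 5.
- Visit 3: 60.5 + 168 = 228.5 days = 7.51 months. The protocol says about 8.

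Both agree with the schedule.

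**Range of ages**

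| Visit | Entry | Earliest | Latest |
|---|---|---|---|
| 2 | 31-90 d | 31 + 84 − 10 = 105 d (3.45 mo) | 90 + 84 + 10 = 184 d (6.05 mo) |
| 3 | 31-90 d | 31 + 168 − 10 = 189 d (6.21 mo) | 90 + 168 + 10 = 268 d (8.80 mo) |
| 3 | 28-84 d | 28 + 168 − 10 = 186 d (6.11 mo) | 84 + 168 + 10 = 262 d (8.61 mo) |

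**Literal reading (norms end at 6.0 months).** The earliest Visit 3 (day 189, or day 186) is already past 182.6 days, so 100% fall outside. No assumption about the spread of entry ages is needed. To be inside at the earliest permitted Visit 3, an infant would have to enter at 182.6 − 158 = 24.6 days or younger, which is not eligible. Visit 3 lies between 189 − 182.6 = 6.4 and 268 − 182.6 = 85.4 days past the limit, with a median of 228.5 − 182.6 = 45.9 days.

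**Generous reading (norms run to the 7-month birthday, 213.06 days).** This assumes entry ages spread evenly in whole days.

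- Entry 31-90 days, visit on the nominal day: outside if entry is at 46 days or later, 45/60 = 75%. Spreading visits evenly over the window also gives 75% (76% in continuous time).
- Entry 28-84 days: 39/57 = 68% (70% in continuous time).
- Entry 31-90 days, every visit at −10 days: outside if entry is at 56 days or later, 35/60 = 58%.
- Entry 31-90 days, every visit at +10 days: outside if entry is at 36 days or later, 55/60 = 92%.

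**Primary outcome.** Visit 2 passes 182.6 days only for entry on day 89 at +10 days, or on day 90 at +9 or +10 days. That is 3 of 60 × 21 = 1,260 combinations, or 0.2%.

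**Size of the error.** The documents give no figure. For illustration only, an assumed mean error of 0.1, 0.25 or 0.5 z moves each group's mean 12-24 week change by the same amount. Relative to the 0.5 z used in the power statement, that is 0.1/0.5 = 20%, 0.25/0.5 = 50% and 0.5/0.5 = 100%. The 0.5 z is a between-group difference at 12 weeks, so it serves only as a yardstick.

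**The case against.** The best reply is that this is a missing scoring rule for a secondary outcome, not an impossibility. Reference 67 may contain a curve that could be extended. The 75%, 68% and 58% figures depend on uniform entry ages: on the nominal visit day, an infant who enters by day 45 is still within 213 days at Visit 3. The illustrative z errors are assumed values. The Table 2 version of the outcome (change from baseline), if compared between groups at the same visit, would largely lose a common norm error. Potential Scientific Problems (IV.E) already concedes that weeks 12-24 have no control group, require assumptions and are secondary. It also points to untreated natural-history infants and healthy local infants as outside comparators.

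Much of this stands as a limit on the size of the problem. It does not remove it. Extending a curve is itself an extrapolation rule, and none is stated. The 100% figure on the literal reading needs no assumption about entry ages. IV.E does not list the age range of the norms among its caveats, and it does not offer the outside comparators as a z-score reference. With no concurrent control, the within-group reading leans harder on the norms. Leptin, weight-for-length and waist circumference at week 24 give partial support, but none of them supplies the missing z-score.

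**Conclusion.** The concern holds and should be fixed. The single named source does not cover any in-window Visit 3 on the literal reading. On the generous reading it fails to cover about 75% (68% for entry at 28-84 days), given uniform entry and window use. The week-24 %BF z-score therefore cannot be derived as written for most or all infants.

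The effect is confined to secondary results, chiefly the within-group 12-24 week change and comparisons across treatment periods. Those readings would be limited even with perfect norms. The finding rests on the protocol's own statement of the norms' age range, as the cited reference was not consulted. The size of any bias is unknown. The week-12 primary outcome is essentially untouched.

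**What to change.** Before unblinding, state that reference 67 z-scores will not be applied at Visit 3, and keep that reference for the week-12 primary outcome. Then adopt one of the following.

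- **(a) One covering reference.** If a suitable %BF reference reaching about 9 months exists, name it and score both ends of the week-24 change with it: from about 3.5 months for the 12-24 week change, and from 1 month for change from baseline. Using it at both ends prevents a switch of reference from being read as a change in the infants. The text change is one sentence. The documents do not show that such a reference exists, and each infant would have two week-12 z-scores, one for the primary and one for the secondary outcome.
- **(b) Absolute %BF at week 24.** Add a week-24 version of the absolute-%BF regression already planned for week 12, with randomised sequence, baseline %BF, age at visit (in place of age at enrolment) and feeding method. Report it as early versus late testosterone. This adds one time point to a planned model. It addresses timing, not benefit over no treatment, and supplements the planned within-group questions.

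Keep the within-group 12-24 week changes. If no covering reference is named, report them in absolute %BF as descriptive only, because they mix normal change with age and any treatment effect. In that case the z-score scale is lost at week 24. Raw %BF is measured at Visit 3 in any case, so neither option needs extra visits, infants or measurements.
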